General aim and endpoint: To assess study feasibility and provide estimated effect sizes (point estimates with confidence intervals) for all measures of interest in order to plan an adequately powered study. We will assess recruitment rates and acceptability of treatment in arms involving exclusive enteral nutrition.

Primary outcome and endpoint: To assess the efficacy of 6 weeks of ECS in inducing remission (CDAI <150) compared to treatment with CS in adult patients with active CD (CDAI >220 and either CRP >5 or fecal calprotectin >250 mg/l).

Secondary outcomes and endpoints: To determine the beneficial effect of 6 weeks of ECS as compared to CS in inducing:

1. Clinical disease improvement (drop in CDAI >70 or 100)
2. Improvement in quality of life (using the Inflammatory Bowel Disease Questionnaire (increase IBDQ scores))
3. Biochemical remission (normalization of either serum CRP and/or fecal calprotectin)
4. Changes in microbiota composition (16S sequencing Illumina)
5. Normalization of colonic transit (SHAPE 0-5 markers at day 5)³⁴ among those with altered transit at baseline
6. Decrease in anxiety and/or depression scores (decrease >2 points HAD-A and/or HAD-D scores)
7. Increase in body weight and improvement in nutritional status (increased levels of micronutrients)
8. Decrease of indirect markers of mucosal integrity (IFABP2)
9. Changes in bacterial fermentation profile (SCFAs: acetate (acetic acid), propionate (propionic acid), and butyrate (butyric acid))^{26,27}.
10. Decreased number of adverse events

METHODS

Study design

Protocol date: October 2018

Randomized control trial; 3 arms of treatment: EEN plus standard or short course of CS (ECS, ECSC) vs CS alone (CS) conducted at McMaster University Medical Centre (Figure 1). The study will last 10 weeks and will involve 4 visits. At the screening visit, we will assess clinical history and symptoms, perform a physical exam and complete bloodwork after the informed consent is signed. Randomization will occur at the second visit (pre-treatment), when the inclusion and exclusion criteria and symptoms will be re-assessed, and baseline stool and urine samples will be collected. In addition, we will perform a SHAPE study and patients will be assessed by a dietitian or clinical nutrition support specialist to assess dietary factors and estimate energy needs using the Harris Benedict equation as detailed below.

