Patients will be instructed to take the allocated treatment and to collect empty bottles/blisters of medication to assess the compliance at the next visit. Six weeks later (visit 3), their symptoms will be re-assessed, blood, urine and stool samples collected and SHAPE study performed. Patients will be instructed to stop the EEN or decrease the dose of CS, as detailed in the section “Follow up after treatment”. In the last visit (4th visit; 10 weeks after enrollment) we will collect information on symptoms, stool samples and urine.

The study protocol will be submitted by the investigator for approval by the Hamilton Integrated Research Ethics Board (HiREB).

Randomization process

The sequence of the treatments will be randomly generated using a computer-based pseudo-random number generator (RStudio Team (2015). RStudio: Integrated Development for R. RStudio, Inc., Boston, MA) Patients will receive one of challenges A,

B, or C consisting of CS, ECS or ECSC. A third person not involved in the study will perform the randomization to preserve treatment allocation concealed from participants and study staff. A block randomization will stratify patients by disease location (colonic/small bowel involvement). Each treatment will be assigned a number according to the randomization sequence. On recruitment, the patient will be assigned into one of three strata and given the next consecutive randomization number available for that stratum. Treatment will be not blinded for patients or study staff.

Subject recruitment

Subjects will be recruited from McMaster University Medical Centre (MUMC) Digestive Diseases Clinic, identified in an ongoing database organized in 2008 and by recruitment flyers posted at McMaster University Medical Centre, Juravinski Hospital and Hamilton General Hospital. Patients in the database signed an informed consent agreeing to be contacted for future research. Patients will be contacted by study personnel and invited to participate in the study.

After the subject has provided written consent to participate, an inclusion checklist will be completed. Subjects will be enrolled after having fulfilled all inclusion criteria, and none of the exclusion criteria.

Participants

One hundred adult patients diagnosed with IBD will be recruited at McMaster University Medical Centre. This will provide 30 subjects in each treatment arm, allowing for 10% dropout rate.

Inclusion criteria:

1. Adult patients (age 18-75 years)

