- Systemic priming to gut bacteria ([name] Lab using Flow cytometry after incubating patients' serum with cultured fecal bacteria¹⁶)
- First urine morning for metabolomics
- Intestinal permeability – indirect markers of mucosal integrity (FABP2)

Statistical analysis

There is no previous estimate on the effect of ECS compared to CS in inducing symptomatic improvement and associated changes in gut microbiota composition. Therefore, a sample size of 30 patients per arm^{28,29} should be sufficient to estimate the results and allow us to plan for future larger study. We will recruit additional 10 patients in total, to account for drop outs rates. Results will be analyzed as intention to treat (for primary outcome) and per protocol (excluding patients non-compliant with EN). The results will be expressed as n (%), mean (SD) or median (IQR) as appropriate. We will perform logistic regression to assess the association between symptomatic response and significant changes in gut microbiota composition in each group. T test or Man Whitney U test will be used as appropriate to assess differences between means. Analysis will be performed using SPSS version 21 (San Diego, CA).

Early withdrawals:

The following criteria will be considered as reasons for early discontinuation from the study (drop outs):

- Patient's decision.

- Physician's decision in case that the continuation of the patient in the study places him/her at risk.
- Patients that were not compliant with the unauthorized concomitant diets/treatments/medication will be considered as non-compliant and considered for the ITT analysis. If a subject's outcome measures worsen to the degree that they meet the study's Exclusion Criteria, study treatment will be withdrawn. Medical care will be provided as directed by the study physician and/or the subject's physician. If the required medical care conflicts with the study protocol, the subject will be placed in the intent-to-treat group. Study safety follow up will continue unless the subject withdraws, and/or is withdrawn by the study physician, and/or on the advice of the subject's physician.

Handling of adverse events

Reporting and documentation of adverse events

All adverse events occurring during the study will be reported and recorded whether or not they are considered to be non-serious, serious and/or related to the treatment. The following information will be required in each case:

- Subject and date
- Description of event
- Duration
- Frequency

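### The named tests for means use neither the randomisation stratum nor the collected baselines, and no method is named for comparing remission between ECS and CS; ANCOVA and a stated risk difference would fill both gaps at little cost

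*Combined protocol and SAP*

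**What the plan says.** All references are to the combined protocol and SAP.

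- *General aim and endpoint*: beside feasibility, the pilot is to "provide estimated effect sizes (point estimates with confidence intervals) for all measures of interest".
- *Primary outcome and endpoint*: a binary outcome, remission (CDAI below 150) after six weeks, ECS against CS.
- *Statistical analysis*: "T test or Man Whitney U test will be used as appropriate to assess differences between means". The only regression is this: "We will perform logistic regression to assess the association between symptomatic response and significant changes in gut microbiota composition in each group". Results are to be summarised as counts and percentages, means or medians. No covariate, stratum term or interval method is named.
- *Randomization process*: "A block randomization will stratify patients by disease location (colonic/small bowel involvement". A few lines later, "the patient will be assigned into one of three strata".
- *Measurements before and after treatment*: the list includes CDAI, quality of life, weight, micronutrients and the mucosal-integrity marker. *Study design* has stool and urine taken at baseline and again at week 6.
- *Secondary outcomes and endpoints*: most are worded as movement from baseline, for example "Increase in body weight and improvement in nutritional status (increased levels of micronutrients". Some are thresholds, for example "Clinical disease improvement (drop in CDAI >70 or 100".

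**The concern.** Two things are missing from the analysis plan.

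First, a two-sample t or Mann-Whitney test takes no covariate. Disease location was judged important enough to stratify on, and baseline values will be on file. Leaving both out gives wider intervals than the data allow. The pilot's estimates are meant to plan the full trial, so interval width is part of what it delivers.

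Second, the primary outcome is a proportion, and no named method is designated to compare it between ECS and CS. The logistic regression does not do so: it is fitted within each group, and its regressor is microbiota change, not treatment. Percentages by arm are description. Confidence intervals are promised, but the scale and the interval method are left open.

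**Working it through.** **Inputs from the protocol.** There are three arms of 30, with 10% dropout and 100 recruited. This reproduces: 3 × 30 = 90 and 90 / (1 − 0.10) = 100. The ECS versus CS comparison therefore has 60 patients.

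**Assumed inputs.** The protocol gives no value of r, no prognostic odds ratios and no ECS or CS remission rates. The values below are ranges or illustrations, with two-sided 95% intervals and equal variances at baseline and week 6.

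**Continuous outcomes.** Relative to the variance of the week-6 value, the variance is 1 for a week-6-only test, 2(1 − r) for a change score and 1 − r² for ANCOVA. The large-sample interval ratios are therefore:

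- ANCOVA / change score = √[(1 − r²) / (2(1 − r))] = √[(1 + r)/2]
- ANCOVA / week-6 only = √(1 − r²)

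The covariates must be paid for. Residual degrees of freedom fall from 58 to 56 with two locations or 55 with three, so the t critical value moves from 2.0017 to 2.0032 or 2.0040. Chance baseline imbalance adds a little to the SE. Simulation (3,000 trials, 30 per arm, useless baseline and location) puts the total at a factor of 1.010, which multiplies both ratios.

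| r | vs change, large sample | × 1.010 | narrower by | vs week-6 only, large sample | × 1.010 | narrower by |
|---|---|---|---|---|---|---|
| 0.3 | 0.806 | 0.814 | 18–19% | 0.954 | 0.963 | 4% |
| 0.5 | 0.866 | 0.875 | 13% | 0.866 | 0.875 | 13% |
| 0.7 | 0.922 | 0.931 | 7% | 0.714 | 0.721 | 28% |
| 0.8 | 0.949 | 0.958 | 4% | – | – | – |
| 0.9 | 0.975 | 0.984 | 1.6% | – | – | – |
| 0.95 | 0.987 | 0.997 | 0.3% | – | – | – |

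Direct simulation at r = 0.3, 0.5 and 0.7 agrees: 0.814–0.815, 0.874–0.876 and 0.930–0.931 against change; 0.964, 0.873 and 0.721–0.722 against week-6 only. At r = 0 ANCOVA is 1% wider than the week-6-only test. Against change scores the ratio reaches 1 where (1 + r)/2 = 1/1.010², that is r ≈ 0.96. Above that ANCOVA is wider by at most about 1%.

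**Primary outcome.** Take 24/30 against 18/30 as an illustration. The Wilson limits are 0.627 to 0.905 and 0.423 to 0.754. Newcombe's limits for the difference of 0.20 are:

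- lower: 0.20 − √[(0.800 − 0.627)² + (0.754 − 0.600)²] = −0.03
- upper: 0.20 + √[(0.905 − 0.800)² + (0.600 − 0.423)²] = 0.41

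Simulated change in the SE of the risk difference with adjustment:

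- Baseline CDAI, standardised from a logistic model that also holds the stratum: +1% to −4% at an odds ratio per SD of 1 to 2, and −7% to −11% at 3.
- Stratum alone, two equal strata: under 1% lower at a stratum odds ratio of 1.5, about 5% at 4, and 7–9% at 6.
- Linear model with baseline and three strata, by correlation of baseline with the latent outcome: 1–2% lower at 0.3, 6–7% at 0.5 and 14–18% at 0.7.

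In those settings a percentile-bootstrap interval for the standardised difference covered 93.0–94.5%, and Newcombe covered 94.4–96.6%.

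**The case against.** The strongest reply is that leaving out covariates is not an error. That stands. Randomisation protects the comparison. In null simulations of the unadjusted and adjusted analyses, rejection rates ran from 3.0% to 5.6%, and the unadjusted t test fell to 3.0% under a strong stratum effect, which is conservative. A reader might infer that the planned analysis is biased or invalid; nothing in the protocol supports that.

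A second reply is that baseline is already used. That largely stands too. Quality of life, weight, micronutrients, the mucosal marker and the fermentation profile are all worded as an increase, decrease or change, so a test on change is the natural reading, although *Statistical analysis* does not say so. The change-score column is therefore the one to quote. A reader might take 28% as the general gain, but that needs a week-6-only analysis, which the outcome wording does not suggest. For body weight over six weeks r of 0.9 or more is plausible, and the gain is then under 2%.

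Third, adjustment does little for the primary outcome under most assumptions, and the bootstrap interval undercovers slightly. This also stands, and it makes the adjusted risk difference optional.

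Fourth, outcomes defined by thresholds (CDAI drop, HAD decrease, normalisation of CRP or calprotectin) are not reached by ANCOVA. Agreed; no gain is claimed for them.

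Finally, one might add the entry criteria to this point. The primary outcome describes patients "in adult patients with active CD (CDAI >220 and either CRP >5 or fecal calprotectin >250 mg/l", whereas *Inclusion criteria* also admits on HBI or endoscopy. Those passages must be reconciled, but that is a separate point and does not add to this one.

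**Conclusion.** The point holds as a matter of precision and specification. The named tests adjust for nothing, and the primary comparison has no named method. For continuous outcomes ANCOVA is expected to narrow change-score intervals by about 18–19% at r = 0.3, 13% at 0.5, 7% at 0.7 and 4% at 0.8, with almost nothing to gain from 0.9 upwards; the worst case is about 1% wider. For remission the SE gain is a few per cent under most assumptions and exceeds 10% only if the baseline is strongly prognostic. All of this rests on assumed correlations and odds ratios. The part that needs no assumption is that remission, the primary outcome, should have its scale and interval method stated in advance, the more so because treatment is not blinded. The change is worth making, but the plan is not invalid without it.

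**What to change.** 1. List the levels of the location factor. *Randomization process* gives two labels but three strata, and a stratum term cannot be specified until this is settled.
2. For outcomes analysed as continuous (quality-of-life score, weight, micronutrients, IFABP2, SCFAs), replace the t or Mann-Whitney test with ANCOVA of the week-6 value on arm, baseline value and disease location, ECS versus CS, with 95% intervals. The arm effect is the same if change is the response, so the outcomes can still be reported as changes. Name in advance which markers are log-transformed (IFABP2 and SCFAs are candidates); do not decide this from the observed skewness.
3. For the primary outcome, report the ECS versus CS risk difference in remission with a Newcombe 95% interval. The same interval serves the threshold-defined secondary outcomes. A risk difference standardised over location and baseline CDAI may be added as a sensitivity analysis.

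Cost: SAP wording and minor analysis work, with 2–3 degrees of freedom out of 58 and no new patients, visits or assays. The change does not settle how a missing week-6 CDAI is handled, or how ECSC is compared with ECS.

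### Stopping treatment is not separated from leaving the study, so the week-6 CDAI needed for the ITT remission analysis is not secured, and no rule covers a missing value

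*Combined protocol and SAP*

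**What the plan says.** The Early withdrawals section introduces its list with "The following criteria will be considered as reasons for early discontinuation from the study (drop outs". Three items follow:

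- the patient's own choice;
- a physician's judgement that remaining would be unsafe;
- a third item, which reads "Patients that were not compliant with the unauthorized concomitant diets/treatments/medication will be considered as non-compliant and considered for the ITT analysis". The wording of this item is garbled. I read it as breach of the restrictions on other diets, treatments or medication.

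The text after the list is mixed. For patients whose outcomes "worsen to the degree that they meet the study's Exclusion Criteria, study treatment will be withdrawn", only treatment is said to end. It adds: "If the required medical care conflicts with the study protocol, the subject will be placed in the intent-to-treat group". On what happens next it says "Study safety follow up will continue unless the subject withdraws", and it also ends that follow-up when the study physician withdraws the patient or the patient's own physician advises it. The CDAI is not mentioned.

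Elsewhere, Statistical analysis makes ITT the approach for the primary outcome and adds a per-protocol analysis that leaves out patients non-compliant with EN. The primary outcome is remission, CDAI below 150, after 6 weeks, ECS against CS. Study design places symptom re-assessment at visit 3, six weeks after the pre-treatment visit. On numbers, Participants recruits 100 and states: "This will provide 30 subjects in each treatment arm, allowing for 10% dropout rate".

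**The concern.** An ITT comparison of remission needs, for every randomised patient, either a week-6 CDAI or a stated rule for its absence. The plan guarantees neither for patients who fall under Early withdrawals. A site that follows the list literally would record a non-compliant or physician-withdrawn patient as out of the study, continue safety follow-up at most, and have no instruction to obtain the CDAI at visit 3. Assigning that patient to the ITT set afterwards does not create an outcome.

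The loss need not be balanced. ECS and ECSC patients must live on formula alone for six weeks, whereas CS patients keep their regular diet, and treatment is open-label. If patients who cannot tolerate the formula leave and would mostly not have remitted, the remaining ECS patients look better than the randomised group. The per-protocol analysis cannot correct this, because its exclusion for EN non-compliance can apply only to the EEN arms.

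The pilot exists to supply effect estimates with confidence intervals for planning the full trial. A biased ECS minus CS difference would pass directly into that planning.

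**Working it through.** **1. The plan's own figure.** Three arms of 30 give 90. Allowing for 10% dropout, 90 / (1 - 0.10) = 100, which equals 90 + 10. The stated 100 reproduces. The allowance is 10 / 3 = 3.3 patients per arm, one rate for all arms. The plan gives no dropout by arm and no alpha, power or effect size, so everything below rests on assumptions.

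**2. Is the week-6 CDAI secured?**

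| Group | Status in the plan | Week-6 CDAI after the event |
|---|---|---|
| Patient's decision | Leaves the study | Not mentioned |
| Physician's decision | Leaves the study | Not mentioned |
| Breach of diet/medication restrictions | Listed as a drop-out, yet kept for ITT | Not mentioned |
| Worsening to meet an exclusion criterion | Treatment withdrawn; study status not stated | Not mentioned |
| Below 80% of dose, or a gap of over three days (Treatment compliance) | Labelled non-compliant only | Visit 3 presumably applies |

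No section gives a scoring rule for a missing CDAI.

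**3. Possible size.** Assume 33 randomised per arm, 20 remissions in each (20/33 = 60.6%, true difference 0), and the plan's 10 drop-outs split ECS 5, ECSC 4, CS 1, all non-remitters.

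- ECS completers: 20 / (33 - 5) = 20/28 = 71.4%.
- CS completers: 20 / (33 - 1) = 20/32 = 62.5%.
- Apparent difference: 71.4 - 62.5 = +8.9 points, all of it spurious.

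**4. Bounds for the same pattern of missing values.**

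- Worst case for ECS: 20/33 - 21/33 = -3.0 points.
- Best case for ECS: 25/33 - 20/33 = +15.2 points.

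**5. Sensitivity to who drops out.** If drop-outs remit at the same 60.6% as completers, the completers-only difference is unbiased. Scoring missing as non-remission would then cost ECS 0.606 x 5/33 = 9.2 points and CS 0.606 x 1/33 = 1.8 points, a net 0.606 x 4/33 = 7.3 points against ECS.

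**6. A second set of assumptions.** Let completers remit at 60% in both arms (the Background's upper figure for EEN, not a design assumption), with CS dropout at 10%. The completers-only difference is 0. The difference in all randomised patients is:

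| ECS dropout | Drop-outs never remit | 30% of drop-outs remit |
|---|---|---|
| 20% | 0.80 x 0.6 - 0.90 x 0.6 = -6 points | (0.48 + 0.06) - (0.54 + 0.03) = -3 points |
| 30% | 0.70 x 0.6 - 0.90 x 0.6 = -12 points | (0.42 + 0.09) - (0.54 + 0.03) = -6 points |

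The direction is the same: completers-only results would flatter ECS by 3 to 12 points.

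**The case against.** The strongest reply is that the plan never cancels visit 3. Study design schedules it without an exception for patients off treatment, and the promise of safety follow-up does not say that nothing else continues. Keeping non-compliers for ITT, and excluding EN non-compliers from the per-protocol set, make sense only if those patients have outcomes. Compliance is judged largely from returned cans and blister packs at the end of treatment, so many patients would be labelled non-compliant at the very visit that supplies the endpoint. This all stands, and it rules out several stronger readings that a reader might draw:

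- *That the week-6 CDAI is not collected.* The documents do not say so; they are silent and partly contradictory.
- *That every non-compliant patient becomes a drop-out.* The 80% and three-day rule only attaches a label, and worsening patients lose treatment rather than, expressly, study status.
- *That the analysis is in effect of completers.* Inflating 90 to 100 is routine and does not define an analysis set; the stated set is ITT.
- *That losses will fall on the EEN arms, or only there.* No figure supports this. The compliance rule also covers prednisone, and physician withdrawal can occur in any arm.
- *That the bias is much larger.* With 8 ECS and 1 CS drop-outs, completers show 20/25 against 20/32, +17.5 points. That fits the plan's total of 10 only if ECSC, with the same six weeks of formula, loses at most one.

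It is also fair that ECS patients receive the same prednisone regimen as CS patients, so failing the formula does not imply non-remission.

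The gap itself remains. The visit schedule describes patients who are on their allocated treatment, since at visit 3 they are told to stop EEN or reduce CS. The section written for discontinuation says the listed patients leave the study. At best the two conflict, and neither supplies a missing-data rule.

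**Conclusion.** The point holds in this form: Early withdrawals merges stopping treatment with leaving the study, mentions only safety follow-up afterwards, and still keeps non-compliers for the ITT primary analysis. The week-6 CDAI is not secured for these patients and its absence has no scoring rule, so the remission comparison may lack outcomes.

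That losses could be higher in ECS and ECSC is plausible from the dietary burden, but it is not shown by any figure in the plan. The illustrative +8.9 points, with bounds of -3 to +15, depends on the assumed split by arm and on every drop-out being a non-remitter. It falls to zero if drop-outs remit as completers do. The stated total of 100 is unaffected. The matter deserves correction in the protocol because an outcome that was never measured cannot be recovered at analysis.

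**What to change.** 1. Reword Early withdrawals so that physician-decided stopping of treatment, and non-compliance, do not by themselves end study participation. Reconcile the list with the sentences that keep such patients for ITT.
2. State that the visit 3 CDAI, with CRP and fecal calprotectin, is sought from every randomised patient who has not withdrawn consent.
3. Analyse the primary outcome in all randomised patients, with a pre-stated rule for the few CDAI values still missing, for example counted as not in remission. Add best/worst-case bounds as a sensitivity analysis.
4. Report missing week-6 CDAI by arm as a feasibility result, beside the planned assessment of acceptability in the EEN arms.

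The cost is protocol wording and, on the plan's own allowance, contact with about 10 patients for a visit already scheduled. Reported remission rates would be slightly lower. Counting missing as non-remission can itself work against the arm with more losses (about -7 points in the example if drop-outs remit at 61%), which is why the bounds should accompany it.

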- Intensity
- Seriousness
- Action taken

Protocol date: October 2018

- Outcome and sequel
- Relationship to test product

Documentation of all adverse events includes completion of the appropriate section of the case report form (AE). Documentation of a serious adverse event that requires a separate form (SAE) will be completed by the investigators in each case.

If further information or examinations are required to assess the relationship between an adverse event and treatment following the occurrence of the adverse event, all examinations or laboratory findings will be noted with their results in the CRF (section UV) or attached to a follow up file. Notification of the HiREB will also be performed in the event of an SAE during the clinical trial.

Estimated length of study: 2 yrs

REFERENCES

- 4-Ruemmele FM. Role of Diet in Inflammatory Bowel Disease. *Ann Nutr Metab*. 2016;68 Suppl 1:33-41. doi: 10.1159/000445392. Epub 2016 Jun 30
- 10-Grover Z, Burgess C, Muir R et al. Early Mucosal Healing with Exclusive Enteral

Nutrition is Associated with Improved Outcomes in Newly Diagnosed Children with Luminal Crohn's disease. *J Crohn's Colitis* 2016; 1-6

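### Safety follow-up may end when a physician takes a patient out of the study, so new adverse events after that point may go unrecorded (a small gap)

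*Combined protocol and SAP*

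**What the plan says.** The combined protocol and SAP deals with this under Early withdrawals. Among the reasons for leaving the study it lists "Physician's decision in case that the continuation of the patient in the study places him/her at risk". It then treats worsening disease separately: if a patient's "outcome measures worsen to the degree that they meet the study's Exclusion Criteria, study treatment will be withdrawn". Medical care is then provided as the study physician or the patient's own physician directs.

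The rule on safety follow-up closes that paragraph: "Study safety follow up will continue unless the subject withdraws, and/or is withdrawn by the study physician", continuing "and/or on the advice of the subject's physician".

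Under Reporting and documentation of adverse events, the collection rule is "All adverse events occurring during the study will be reported and recorded", and each report includes "Outcome and sequel". For serious events, "Notification of the HiREB will also be performed in the event of an SAE during the clinical trial".

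The number of adverse events is item 10 of the secondary outcomes. It is also one half of Hypothesis 2, which expects fewer events with the short steroid course (ECSC) than with the standard course plus formula (ECS).

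**The concern.** A patient's own decision to leave is a proper reason to end follow-up, and it is not questioned here. The other exceptions are different. They allow safety follow-up to end on a physician's action or advice, and the sentence names no decision by the patient for them.

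Risk to the patient is a good reason to stop the formula, the prednisone or the study procedures. It is not a reason to stop asking about adverse events. If recording ends at that point, the missing follow-up belongs to patients removed on safety grounds, so the loss may be related to the outcome being counted. The general aim is to supply effect estimates with confidence intervals for all measures of interest, to plan a larger study. Adverse events are one of those measures.

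**Working it through.** The question is one of wording, so the check is whether any other text restores what the follow-up sentence allows to stop.

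1. **Who is affected.** A patient who loses only study treatment, for example after worsening into the exclusion criteria, keeps safety follow-up by default. The exceptions reach patients whom the study physician withdraws. On the plainest reading they also reach patients for whom their own physician advises stopping.

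2. **General adverse event rule.** Collection is tied to events "during the study" in substance. Early withdrawals classes the physician's decision as discontinuation from the study. The protocol does not say whether such a patient still counts as being in the study, so this rule does not clearly cover later events. The same applies to ethics board notification of serious events, which is tied to the clinical trial period.

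3. **Work-up and outcome of a reported event.** The outcome field, and the further examinations used to judge causality, concern an event that has already occurred. They do not look for new ones.

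4. **Visit 4.** Study design places the last visit at week 10 and lists symptoms, stool and urine. No text says that a physician-withdrawn patient attends.

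5. **Intention-to-treat placement.** A patient whose medical care conflicts with the protocol is placed in the intention-to-treat group. That concerns analysis, and Statistical analysis names intention to treat for the primary outcome. It does not require adverse event collection.

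6. **Medical care.** This is clinical care, not study recording.

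None of items 2 to 6 clearly closes the gap.

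**What can be said about numbers.** The plan's recruitment figure reproduces: 3 arms x 30 = 90, and 90 / (1 - 0.10) = 100. Statistical analysis agrees: "We will recruit additional 10 patients in total, to account for drop outs rates", and 90 + 10 = 100. The allowance is therefore 10 patients over three arms, or 10 / 3 = about 3 per arm, with no split by reason. It is a planning figure, not a limit, and it does not say how many of the 10 would be physician withdrawals.

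Two further inputs are missing. One is when such withdrawals would occur. The other is the period over which adverse events are compared: the secondary outcomes and Hypothesis 2 are framed around six weeks of treatment, while the study lasts 10 weeks. Without these inputs, no share of lost events can be calculated.

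**The case against.** The strongest reply is that the protocol already protects these patients. Follow-up continues by default and survives treatment withdrawal, the triggering event is recorded with its outcome, and medical care is expressly provided. All of this stands. A reader might infer that patients at risk are left without care; the documents do not support that. What may stop is research recording.

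Second, the collection rule could be read as covering all 10 weeks for every randomised patient, whether withdrawn or not. That is possible, but the text does not settle it, and the specific sentence on withdrawal points the other way. Likewise, the clause on the patient's own physician could be a ground for being withdrawn rather than a separate stop. On either reading, follow-up can end through a physician's action.

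Third, if the adverse event comparison is meant to cover six weeks only, recording lost after week 6 would not touch it. This is correct, and it is one reason the size is left open.

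Fourth, the consent pages are not in the available text and may already provide for contact after withdrawal. That cannot be checked, so the point rests on the protocol's wording alone.

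Last, no stated decision would change in a pilot of this size. That is fair, and it is why the point is minor. It does not make the sentence worth keeping when a better one costs so little.

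**Conclusion.** The point holds as a minor one. The follow-up sentence permits safety recording to end for patients whom a physician takes out of the study, including those removed because of risk, and nothing else clearly requires new adverse events to be collected from them. The consequence is a small, possibly informative loss in secondary outcome 10 and in the adverse event half of Hypothesis 2.

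Small is a judgement. It rests on the default that follow-up continues and on the expectation, drawn from the dropout allowance, that few patients would be affected. A reader might go further and infer a percentage of lost events, or a bias towards one arm. The documents support neither: withdrawn patients may have more events than others or may leave early, and nothing indicates which arm would lose more. The primary outcome, remission by CDAI, does not depend on this sentence.

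**What to change.** Replace the follow-up sentence with:

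*Adverse event follow-up continues to week 10 for every randomised patient, including those withdrawn from treatment or study procedures by the study physician or on their own physician's advice, and ends early only if the patient withdraws consent to follow-up contact.*

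This removes both physician exceptions on purpose. A physician can still stop treatment and procedures, and only contact about adverse events goes on. Week 10 matches the last planned visit and the final week of the standard prednisone taper in Figure 1.

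The cost is one protocol sentence, a few extra calls or already planned visits for a handful of patients, and a check that the consent wording allows this contact. No new staff or procedures are needed.
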